### *Exclusion criteria for all Participants:*

- History of head trauma with LOC > 30 minutes, or with a penetrating head wound, or with moderate to severe memory or other cognitive impairment.
- Neurological disorders: multiple sclerosis, epilepsy, stroke, PD, other degenerative CNS disorders, or neuropathy with radicular involvement.
- Acute or chronic major psychiatric disorders: schizophrenia, bipolar disorder or severe major depressive disorder, or severe anxiety disorder except PTSD and panic disorder (PTSD and depressive symptoms are common co-morbid conditions for combat mTBI and a subset of these patients have symptoms consistent with panic disorder as well).
- Use of illegal drugs; alcohol abuse within the past 6 months.
- Poorly controlled hypertension, heart failure, coronary heart disease, peripheral artery disease, carotid artery disease, diabetes mellitus, pulmonary disease with hypoxia or hypercapnia,

significant hepatic disease or hepatitis C seropositivity, renal failure, treatment for cancer, HIV positive, active infectious disease or presence of abdominal aortic aneurysm.

- Contraindications to LP (e.g., spinal cord injury; deformity, severe disease or infection in the region of the lumbosacral spine; bleeding tendency, use of anticoagulant medications, or platelet count <100,000/mm^2).
- Receiving medication in an investigational drug study.
- Exclusionary medications (used in the 4 weeks prior to screening):
  - Fibrates and niacin due to increased risk for myopathy in combination with statins;
  - Potential drug-drug interactions with statins via effects on CYP3A4: itraconazole, ketoconazole, erythromycin, clarithromycin, HIV protease inhibitors, nefazodone, amiodarone, cyclosporine, isoniazid, quinidine, or large quantities of grapefruit juice (>1 quart daily);
  - Selected CNS-acting medications: antipsychotics, anti-Parkinson's disease medications and CNS stimulants
  - Other medications affecting coagulation and/or inflammation: coumadin, potent anti-inflammatory medications (hydrocortisone, methotrexate or other potent immune-modulating medications), and anti-HIV medications.
- All female subjects of childbearing potential will undergo a urine pregnancy test at every subject visit; subjects with positive pregnancy test results will be excluded. In addition, all female subjects of childbearing potential will be required to use a reliable method of contraception throughout the duration of the study.

Description of Recruitment Process: Participants will be recruited from the MIRECC Mild TBI/Behavioral Specialty Clinic; Deployment Health Clinic, Polytrauma Clinic, General Internal Medicine Clinic, and Mental Health Clinics at VA Puget Sound; the Seattle downtown Vet Center; community-based outpatient clinics (CBOCs), and from outreach to National Guard and Reserve units. Recruitment will be assisted by posters, flyers, brochures, announcements in the VA daily bulletin, and print and radio media advertising. Prospective participants will have their charts reviewed by referring providers to screen for exclusionary medical conditions and medications.

Potentially eligible persons will be referred to the study team for obtaining informed consent. Written informed consent will be obtained from participants by the PI, study Co-Investigator, or Study Coordinator. If a potential participant's primary mental health care provider is a study investigator, another investigator will conduct the consent process. Care will be taken to assure participants that research study participation is voluntary and their current treatment and future services and benefits are not contingent on participation in this or any research study.

Participants will receive compensation for their time and inconvenience as follows: \$50 for the screening visit, \$50 for each cognitive testing day, \$200 for each LP day, and \$25 for each safety visit. The total each subject will receive if all study visits are completed is \$650. Subjects who withdraw early or are withdrawn from the study will receive pro-rated payments based on the number of study visits completed.

Inclusion of Women and Minorities: Because of the requirement that blast trauma group participants have experienced at least one blast trauma exposure, the majority of participants in this group will come from Military Occupational Specialties (MOSs) with high blast trauma exposure: Infantry, Combat Engineers, Explosive Ordnance Disposal, and Military Police (MP). Infantry, Combat Engineers, and Explosive Ordnance Division are all male combat MOSs. It is estimated that fewer than 25% of the MP MOS participants will be women based on the gender composition of the Military Police who served in Iraq and Afghanistan. Although it is not anticipated that we will have sufficient numbers of women subjects to have adequate power to detect gender effects on study outcomes, gender will be used as a stratification variable during the randomization to ensure that women subjects have an equal chance of receiving active drug. Persons of all races and ethnic backgrounds will be eligible. The veteran patient population at VA Puget Sound is comprised of 75% Caucasians, 14% African Americans, 4% Native Americans, 3% Hispanic Americans, 2% Asian Americans, and 2% "other". No differences based on racial/ethnic differences are expected.

### **Study procedures:**

There will be a total of nine study visits over a period of 12 months, including the screening visit, four visits for monitoring adverse effects and compliance, and four visits for measuring study outcomes (two at Baseline and two at 12 months). Table 3 below outlines all study visits.

Screening visit: Screening for eligibility will include a brief cognitive screen with the Montreal Cognitive Assessment (MoCA). Detailed medical and psychiatric history, current medications, and medications used over

past 6 months will be reviewed. Potential participants will be administered the Structured Clinical Interview for DSM-IV--Patient Edition (SCID-IV) to diagnose exclusionary psychiatric disorders.

Table 3. Detailed Schedule of Study Visits

	Screen Visit	Baseline Visits		Safety Visits				12 mo Outcome	
		1 st	2 nd	6 wk	3 mo	6 mo	9 mo	1 st	2 nd
Demographics	X								
Medical/psychiatric/military history	X								
Physical/neurological examination	X							X	
CBC, Chem 7, TSH, B12, folate, albumin, routine urinalysis	X								
fasting lipid panel (HDL, LDL, triglycerides)	X	X						X	
Plasma homocysteine & C-reactive protein (CRP)		X						X	
LFTs, bilirubin, CPK, HbA1c	X			X	X	X	X	X	
Urine pregnancy test	X	X	X	X	X	X	X	X	X
APOE genotype	X								
LP – CSF biomarkers		X						X	
SCID-IV	X								
CAPS, SWLS			X						X
PCL-M, PHQ-9, AUDIT-C			X	X	X	X	X		X
MoCA	X		X	X	X	X	X	X	
Neuropsychological test battery			X						X
Vital signs	X	X	X	X	X	X	X	X	X
Review of concurrent medications	X	X		X	X	X	X	X	
Assess adverse events			X	X	X	X	X	X	X
Pill count for med compliance				X	X	X	X	X	
Dispense study medications			X	X	X	X	X		

A complete physical and neurological examination will be performed. Screening laboratory tests will be obtained, including complete blood count (CBC), chemistry panel, thyroid stimulating hormone (TSH), vitamin B12, folate, SGOT, SGPT, SGGT, bilirubin, alkaline phosphatase, CPK, albumin, and fasting lipid panel (total cholesterol, HDL, LDL, and triglycerides), urinalysis, and (in female subjects of childbearing potential) a urine pregnancy test. Blood samples will also be collected for apolipoprotein E (APOE) genotyping (described below). A urine sample will be obtained for routine urinalysis and (in female subjects of childbearing potential) a urine pregnancy test.

**Baseline:** The Baseline visit will be scheduled within 4 weeks of the Screening visit. The Baseline visit consists of 2 separate appointments within a week of each other. During the first visit, vital signs will be obtained, a brief physical examination will be performed, concurrent medications will be recorded, a blood draw will be performed for measurement of plasma lipids and inflammatory markers, and an LP will be performed as described in detail below.

During the second baseline visit, the neurocognitive test battery will be administered and behavioral assessments will be performed. Comorbid PTSD will be assessed with the CAPS. A detailed description of all study instruments is below.

**Randomization, titration, and continued study treatment:** Upon completion of all baseline procedures, participants will be randomized to receive simvastatin or placebo. Stratification factors will include age (<40 vs ≥ 40 years), gender, and number of blast trauma exposures (<5 and ≥5). Permuted block randomization will be used within each stratum. Varying the block size reduces the predictability of treatment assignment. Separate blocked sequences will be generated for each of the three strata and provided directly to the Research Pharmacist at the VA Puget Sound, who will prepare study drug for dispensing.

Simvastatin will be started at 20 mg qhs and titrated over 2 weeks to a final dose of 40 mg qhs. Placebo will be titrated at week 2 correspondingly. We assume a drop-out rate of ten percent, yielding a total sample size of 50 subjects per group at the end of the study.

**Safety and compliance visits:** Four additional visits will be scheduled at 6 weeks and at 3-, 6-, and 9-months of treatment to monitor adverse effects, assess compliance with study medications, and dispense study medication. Each visit will include measurement of vital signs, update of concurrent medications, and any self-report of adverse effects. Pill counts will be used to assess compliance. Safety assessments as described below will be performed.

**Outcome assessment:** Outcome assessments will be obtained in two visits at the end of 12 months of treatment. Procedures for outcome assessments duplicate the procedures performed during the Baseline visits as described above. Pill counts will be used to assess compliance with medication use.

**Monitoring safety of participants:** Simvastatin is used widely for lowering cholesterol and for primary prevention of cardiovascular and cerebrovascular disease at the doses proposed in this application. It is generally safe and well tolerated. The rate of adverse reactions necessitating withdrawal from statin therapy is <1% in clinical practice. The most common adverse effects in clinical use are elevated liver transaminases, myalgias, and elevated CPK. In our pilot study, all subjects tolerated a final simvastatin dose of 40mg/day. Of 24 subjects recruited, only two had significant adverse effects in response to statin therapy. One experienced significant myalgias requiring discontinuation of therapy despite a non-significant elevation in CPK. Another exhibited a slight increase in CPK with statin therapy. Mean serum CPK concentrations increased marginally over the course of the study. Mean SGOT and SGPT values increased equivalently. Only one subject developed a significant, though asymptomatic, elevation in SGPT. None of the subjects in our pilot study nor in our current placebo-controlled trial of simvastatin for primary prevention of AD experienced adverse cognitive changes or psychiatric symptoms.

Subjects will be advised of potential drug-related side effects such as muscle pain and weakness and nausea or vomiting at both the Screen (consent process) and Baseline visits. In addition, subjects will be monitored at 6 weeks and at 3-, 6-, 9-, and 12 months of treatment for potential adverse events. At each visit, we will review symptoms of anticipated adverse effects (such as muscle pain, weakness, and nausea), measure LFTs, CPK, and HbA1c, and (for female subjects of childbearing potential) conduct urine pregnancy tests.

To monitor for potential cognitive side effects, we will perform the MoCA (a brief but sensitive global cognitive test) at all safety visits. If a subject reports problems with memory or cognitive function after initiation of study medication sufficient to interfere with daily function or MoCA score decline of one standard deviation or greater compared to Baseline, we will perform a thorough neurological and psychiatric examination and will administer the entire neuropsychological battery. If a decline of one standard deviation or greater compared to Baseline is present on two neuropsychometric measures, the subject will be terminated from the study.

To monitor for emergence or worsening of comorbid depression, the PHQ-9, a self-report measure of depression will be administered at all visits. The PHQ-9 score can range from 0 to 27. Scores of 5, 10, 15 and 20 represent thresholds demarcating the lower limits of mild, moderate, moderately severe and severe depression, respectively. If the PHQ-9 score is increased by 10 (i.e., an increase of two severity categories) compared to baseline, the subject will be terminated from the study. To monitor alcohol use and symptoms of comorbid PTSD, we will administer the AUDIT-C and the PCL-M at all visits.

If at any time during the study, a participant complains of symptoms which may indicate a potential adverse event, additional safety visit(s) as necessary will be performed. Procedures to be performed at additional visits will depend on the symptoms the participant is experiencing. If the participant meets any criterion for study removal (as described below), an early discontinuation visit will be performed.

**Early treatment discontinuation procedures:** The primary reasons for treatment discontinuation anticipated during the study are adverse effects, protocol violation, noncompliance, and withdrawal of consent. We will make every reasonable effort to keep each subject in the study. Every effort will be made to schedule a discontinuation visit as soon as possible following discontinuation of study medication to allow collection of outcome and safety measures.

**Criteria for termination from study:** Subjects will be removed from the study if they: 1) develop a significant adverse medication reaction, including psychiatric adverse effects; 2) exhibit >1 standard deviation decline on more than one component of the neuropsychological test battery; 3) develop a significant elevation in serum transaminases (i.e., > 3 X upper limit of normal for SGOT and/or SGPT) or CPK (i.e., > 10 X upper limit of normal); 4) have a positive urine pregnancy test; or 5) meet NCEP/ATP-III criteria for initiation of lipid-lowering therapy at the 3- or 6-month safety visits.

**Compliance with study medications:** Subjects will be given a 6-week supply of medication at Baseline and at the 6-week visit, and subjects will be given 3-month supplies of medication at the 3-, 6- and 9-month

visits. Pill counts to assess medication compliance will be performed at each safety visit. In our pilot study of simvastatin and pravastatin, 23 (96%) of 24 subjects completed the 3-month study and the completers had taken 94–100% of scheduled doses of medication as assessed by pill counts. The compliance rate in a longer (one year) study might be expected to be lower. However, the 5-year compliance rate was fairly high in the Heart Protection Study. In this study, the rate of compliance (> 80% of scheduled tablets) was 89% at the end of the first year of follow-up and 85% at the end of the second year among participants allocated to take 40 mg simvastatin daily. In this proposed study, we will make a 6-week interim phone contact, in addition to the scheduled study visits, to ensure adequate compliance with study medication. We will make interim phone contact between months 3 and 6, 6 and 9 and 9 and 12, in addition to the scheduled study visits, to ensure adequate compliance with study medication. We expect a compliance rate of 90% over the course of the 1-year study.

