**Behavioral, functional and quality of life measures:** The SCID-IV will be administered at screening only to rule out exclusionary psychiatric conditions. Comorbid PTSD will be assessed using the CAPS at baseline and after 12 months of treatment and the PCL-M at all study visits. Current mTBI symptoms, functional status, and health-related quality of life will be quantified using the Brief Symptom Inventory (BSI), the Rivermead Postconcussive Questionnaire (RPQ), the Neurobehavioral Symptom Inventory (NSI), Satisfaction with Life Scale (SWLS) and the Craig Handicap and Assessment Reporting Technique (CHART-DF). The PHQ-9 and AUDIT-C will be administered at all study visits to assess depressive symptoms and alcohol use.

**Neurocognitive Battery:** We will use measures from the NINDS CDE as well as additional measures for assessment of neurocognitive function. The neurocognitive test battery includes measures of learning and memory, attention and information processing speed, and executive function. In addition, we will employ a measure of test effort (the Test of Memory Malingering [TOMM]) to provide an estimate of the validity of subject's test scores. If a subject's score on the TOMM suggests inadequate test effort, the rest of neurocognitive test scores will be considered invalid. The estimated time to complete the entire test battery is two hours. The complete neurocognitive battery will be administered at baseline and after 12 months of treatment with simvastatin or placebo. A brief global cognitive screening measure (the MoCA) will be administered at screen and at all subsequent study visits to ensure there is no cognitive decline during the study. The study psychometrist will be trained by Co-Investigator, [name]., MIRECC neuropsychologist, and she will conduct periodic checks for adherence to the standardized neuropsychological test battery administration protocol.

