### **Statistical analysis.**

**Primary analysis plan:** All CSF biomarkers, neuropsychological test scores, behavioral assessments, and functional and quality of life measures are continuous variables. Gender, APOE genotype, and number of mTBIs ( $\geq 5$  or  $< 5$ ) are categorical. Analysis of covariance (ANCOVA) will be used to assess the change from the baseline in all biomarkers as well as neuropsychological test scores. All outcomes are continuous variables. The distribution of model residuals will be assessed and outcome variables may be transformed to conform to assumptions of the statistical tests (e.g., for non-normality). The response variables will be biomarker concentrations at the end of the study (12-month visit), and predictor variables will include biomarker concentrations at the beginning of the study (baseline visit), treatment arm assignment (simvastatin vs. placebo), as well as the variables that were used for stratification of treatment assignment (i.e., gender and number of blast exposures). To examine effects of statin treatment on memory and cognition, the response variables will be test scores at the end of the study (12-month visit). The predictor variables will include test scores at the beginning of the study (baseline visit), treatment arm assignment (simvastatin vs. placebo), as well as the variables that were used for stratification of treatment assignment (i.e., gender and number of blast exposures). Significance of treatment arm effect will be adjusted for multiple tests (i.e., the four primary endpoints) using the method of Holm (1979).

The primary analysis will include all subjects who were randomized and completed the study. A secondary analysis will use a linear mixed-effects model to include all subjects who were randomized and had a baseline visit, including subjects with just a baseline visit as well as subjects with a baseline visit and an early termination visit. Baseline differences, if any, between study completers and non-completers will be summarized.

**Secondary analysis plan:** In addition to the above primary analysis, secondary analyses will include the following:

- Correlation analyses to assess relationships among CSF biomarkers and how they change over time relative to each other.
- Exploring what other covariates (such as serum cholesterol levels) may be important in predicting changes from baseline in CSF AD biomarkers

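### The screening MoCA is a second pre-randomisation score that the cognitive ANCOVA leaves unused; adding it as a covariate would bring a free but modest gain in precision

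*Combined protocol and SAP*

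**What the plan says.** Under Study procedures, the screening visit includes the test: "Screening for eligibility will include a brief cognitive screen with the Montreal Cognitive Assessment (MoCA"). Table 3 marks the MoCA at the screening visit and again at the second baseline visit. The Neurocognitive Battery paragraph puts it more broadly: "A brief global cognitive screening measure (the MoCA) will be administered at screen and at all subsequent study visits".

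On timing, "The Baseline visit will be scheduled within 4 weeks of the Screening visit", and the two baseline appointments fall within a week of each other. Treatment is assigned afterwards: "Upon completion of all baseline procedures, participants will be randomized to receive simvastatin or placebo".

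Under Statistical analysis, "Analysis of covariance (ANCOVA) will be used to assess the change from the baseline in all biomarkers as well as neuropsychological test scores". For memory and cognition, "the response variables will be test scores at the end of the study (12-month visit"), and "The predictor variables will include test scores at the beginning of the study (baseline visit), treatment arm assignment (simvastatin vs. placebo"), together with gender and number of blast exposures. The secondary mixed model mentions only baseline and early termination visits, and the exploration of further covariates concerns CSF biomarkers. No analysis uses the screening MoCA.

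**The concern.** A single reading of a short 30-point test is an imperfect predictor of the same person's score a year later. Two readings before treatment usually predict it better, and here the second is already scheduled. Because both come before randomisation, either can be a covariate without biasing the arm effect. A practice gain between them, or selection on the screening score, would affect both arms alike.

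What is at stake is precision in a cognitive safety comparison with about 50 completers per arm. The protocol states no power for any cognitive outcome. Its own section on the risks of simvastatin describes earlier trials of statins and cognition, one of them with 209 subjects, as small and possibly underpowered. In a safety comparison, low power favours the reassuring answer, so it makes sense to use data already collected.

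**Working it through.** **Inputs from the documents.** 120 recruited and about 17% dropout (Sample Size, Effect Size, and Power) give 120 × 0.83 / 2 = 49.8, about 50 per arm. The randomisation paragraph gives 10% dropout, which would mean 54 per arm; the percentage cuts below do not depend on this. The two pre-drug MoCA scores are at most 4 weeks plus 1 week, about 5 weeks, apart.

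**Assumptions.** The documents give no MoCA retest coefficient and no alpha for cognitive tests. I take two-sided 0.05. Let rs be the correlation between the screening and baseline scores, and rl the correlation of each with the 12-month score. Effects are in SD units of the 12-month score.

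**Plan's own figure.** The only stated power is for the CSF endpoints: 80% at 0.68 SD and 90% at 0.77 SD, with 50 per group and alpha 0.05/4 = 0.0125. A two-sided noncentral t calculation gives 80.2% and 90.2%, so it reproduces.

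**Formulas.** The share of outcome variance left after adjustment is:
- one pre-treatment score: V1 = 1 − rl²
- two pre-treatment scores: V2 = 1 − 2·rl² / (1 + rs)

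The proportional cut is 1 − V2/V1, and the equivalent size per arm is 50 × V1/V2. For example, with rs = 0.8 and rl = 0.7: V1 = 1 − 0.49 = 0.510; V2 = 1 − 0.98/1.8 = 0.456; cut 10.7%; 50 × 0.510/0.456 = 56.

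**Results**, with power for a 0.3 SD decline from the noncentral t:

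| rs | rl | V1 | V2 | Cut | Like n per arm | Power, one score | Power, two scores |
|---|---|---|---|---|---|---|---|
| 0.9 | 0.5 | 0.750 | 0.737 | 1.8% | 50.9 | 40% | 41% |
| 0.9 | 0.6 | 0.640 | 0.621 | 3.0% | 51.5 | 46% | 47% |
| 0.8 | 0.6 | 0.640 | 0.600 | 6.2% | 53.3 | 46% | 48% |
| 0.6 | 0.5 | 0.750 | 0.688 | 8.3% | 54.5 | 40% | 43% |
| 0.9 | 0.8 | 0.360 | 0.326 | 9.4% | 55.2 | 70% | 74% |
| 0.8 | 0.7 | 0.510 | 0.456 | 10.7% | 56.0 | 55% | 60% |
| 0.7 | 0.7 | 0.510 | 0.424 | 17.0% | 60.2 | 55% | 63% |
| 0.8 | 0.8 | 0.360 | 0.289 | 19.8% | 62.3 | 70% | 79% |

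The first six rows have rs above rl by at least 0.1, which is plausible when one interval is five weeks or less and the other about a year. Narrower gaps give cuts between the two groups: 0.85 and 0.8 give 1 − 0.308/0.360 = 14%. The last two rows need the short and long intervals to correlate equally.

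**Check by simulation** (10,000 runs, 50 per arm, mean of the two scores as covariate). With rs = rl = 0.6, power for 0.3 SD rose from 45.7% to 51.8%. With rs = 0.8 and rl = 0.6, it rose from 45.9% to 48.1%. With no true difference at 0.8 and 0.6, type I error was 5.0% with one score and 5.2% with two.

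**The case against.** The strongest objection is that the plan may not compare the MoCA between arms at all. The statistical analysis section refers to neuropsychological test scores and to memory and cognition, without naming it. Table 3 lists the MoCA on a different row from the neuropsychological battery, and the safety section uses it as a trigger for giving that battery. On the other side, the Neurocognitive Battery paragraph describes the MoCA, and it is a cognitive score with baseline and 12-month values. Including it is a reasonable inference but remains one. The ambiguity is itself a reason to write the sentence.

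Second, the description of study instruments calls MoCA retest reliability high, with under a point of variation. That gives no coefficient, but it points to a largely redundant second score and so to the lower end of the gain. This stands.

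Third, the effort test that decides whether cognitive scores are valid belongs to the battery, which is not given at screening. A screening MoCA taken with poor effort would be a noisier covariate and would shrink the gain. It would not bias the comparison.

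Three stronger readings are tempting:
- A reader might infer that adjusting for one baseline score is wrong. It is standard and valid, and nothing in the plan is biased by it.
- A reader might infer that the protection of individual participants is weakened. The visit-by-visit MoCA rule compares each person with their own baseline; it is separate from the arm comparison and this point does not touch it.
- A reader might expect the extra score to help a model of the interim MoCA values. The plan contains no such model.

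**Conclusion.** The point holds as an optional improvement. Two pre-randomisation MoCA scores are scheduled and the specified adjustment uses one. Provided the MoCA is an ANCOVA outcome, adding the screening score would cut residual variance by about 2 to 11% if the pre-drug scores correlate more with each other (0.6 to 0.9) than with the 12-month score (0.5 to 0.8), by 0.1 or more. It would reach 17 to 20% only if all correlations are equal at 0.7 to 0.8. All these correlations are assumed.

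In the first case, power for a 0.3 SD decline rises by about 1 to 5 percentage points. That does not make the comparison well powered for small declines: with a 12-month correlation of 0.5 to 0.7, power for 0.3 SD is about 40 to 55% with one score and 41 to 60% with two.

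**What to change.** Add to the statistical analysis section, before unblinding, that the 12-month MoCA is compared between arms by ANCOVA, with the screening score and the second-baseline-visit score both entered as covariates, alongside arm and the other planned covariates. Leave the individual MoCA monitoring rule unchanged.

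While editing, reconcile the Neurocognitive Battery paragraph, which has the MoCA at every visit after screening, with Table 3, which shows none at the first baseline or second 12-month visit. The pre-randomisation scores and the outcome visit are then unambiguous.

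The cost is one sentence and one degree of freedom, with no new data, visit or burden.

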## RESEARCH DESIGN AND METHODS

**Overview:** The proposed study is a 12-month, double blind, randomized placebo-controlled trial of simvastatin (40 mg/day) vs. placebo in Iraq and Afghanistan Veterans with repetitive blast mTBI with PPCS). We will use National Institute of Neurological Disorders and Stroke Common Data Elements (NINCDS CDE) Core and selected Supplemental measures relevant to mTBI from the as well as additional assessments. The study definition of mTBI will follow ACRM criteria, defined as a traumatically induced physiologic disruption of brain function manifested by at least one of the following: loss or alteration of consciousness lasting less than 30 minutes; any loss of memory for events immediately before or after the accident with any posttraumatic amnesia lasting not more than 24 hours; initial Glasgow Coma Scale score  $\geq 13$ . Although most participants will have multiple exposures, they will be considered to have mTBI if any single exposure meets these criteria. Because Glasgow Coma Scale scores in the combat setting will be unavailable, this criterion will not be required if other criteria for mTBI are met.

Primary outcomes are change in concentration of CSF t-tau, p-tau181, p-tau181:t-tau ratio, and BDNF. The secondary outcomes include change in concentration of CSF biomarkers of amyloid deposition: A $\beta$ 42; oxidative stress: F2-isoprostanes; and inflammation: IL-6, IL-8, and S100 $\beta$ . Potential cognitive adverse effects of statin treatment will be assessed by psychometric measures of simple and sustained attention, working and declarative memory, and complex reasoning. Primary and secondary CSF biomarker outcomes and neuropsychological tests will be measured at baseline and 12-months of treatment. Customary clinical monitoring for clinical response and for adverse effects (including CPK and hemoglobin A1C) will be monitored at 6-weeks and at 3-, 6-, 9-, and 12-months of treatment. Compliance will be monitored with pill counts at each visit.

**Participants:** 120 Iraq and Afghanistan Veterans who meet study inclusion/exclusion criteria will be enrolled. Persons of all races and ethnicities and both genders will be eligible. Participants will be naïve for statins, and will have either normal LDL cholesterol or mildly elevated LDL cholesterol which does not require drug therapy per National Cholesterol Education Program Adult Treatment Panel III (NCEP/ATP-III) guidelines.

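### The randomisation section commits to sequences for three strata, but its three two-level factors form eight (four on the two factors named elsewhere), so the number of lists is wrong and must be reconciled before they are made

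*Combined protocol and SAP*

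**What the plan says.** Under Study procedures, in the paragraph on randomization, titration and continued treatment, the plan lists the factors: "Stratification factors will include age (<40 vs ≥ 40 years), gender, and number of blast trauma exposures", with exposures cut at five. It then gives the method: "Permuted block randomization will be used within each stratum". Block sizes vary but are not stated. The next instruction fixes what is produced and who receives it: "Separate blocked sequences will be generated for each of the three strata and provided directly to the Research Pharmacist".

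Two other places describe the stratification differently:

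- The text on sample size, effect size and power speaks of two stratification factors that may influence t-tau, gender and number of blast exposures. It expects the stratification to reduce the variability of the treatment-effect estimate.
- The primary analysis plan puts the stratification variables into the ANCOVA and lists them, in a closed parenthesis, as gender and number of blast exposures. Age is absent. The list appears twice, once for biomarkers and once for cognitive scores.

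The primary analysis plan also opens with a sentence sorting variables by type, in which the categorical ones are "Gender, APOE genotype, and number of mTBIs", cut at five.

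The section on inclusion of women and minorities gives a purpose for one factor: "gender will be used as a stratification variable during the randomization to ensure that women subjects have an equal chance of receiving active drug".

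**The concern.** The sentence that sets the number of sequences is the operative instruction to the pharmacy, and its number does not fit the factors listed just before it. A 35-year-old man with six blast exposures has a level on each of the three factors. If there were one list per factor he would be on all three, and nothing in the plan says which list assigns him. Stratified blocking controls arm balance within a cell only when each cell has its own sequence, so the precision benefit expected in the sample size section depends on this being right.

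The plan also does not settle which number was meant. The randomisation section implies eight; the sample size and analysis sections point to four. A statistician preparing the lists would have to guess whether age is a stratifier, and the ANCOVA as written would omit age if it is.

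**Working it through.** **Inputs.** From the randomisation paragraph: age (<40, ≥40), gender (two levels), blast exposures (<5, ≥5). From the sample size text and the primary analysis plan: gender and blast exposures only.

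**Count of strata.** The number of strata is the product of the numbers of factor levels.

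| Reading | Calculation | Result |
|---|---|---|
| Three factors crossed | 2 × 2 × 2 | 8 |
| Two factors crossed | 2 × 2 | 4 |
| Separate factor levels, not crossed | 2 + 2 + 2 | 6 |
| Stated in the plan | – | 3 |

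The stated figure is not reproduced by any of these. Three is the number of factors.

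**Does the stated power depend on it?** Inputs from the sample size text: 50 per arm, α = 0.05/4 = 0.0125 (taken as two-sided, which the text does not say), effect sizes 0.68 and 0.77 SD. The noncentrality is d × √(n/2) = d × √25 = 5d, that is 3.40 and 3.85. With 98 degrees of freedom the noncentral t gives power of 0.802 and 0.902, matching the stated 80% and 90%. The calculation contains no term for stratification, so the power claim stands whichever number of strata is used.

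**Which exposure count is modelled?** The overview of the design says of participants with several exposures that "they will be considered to have mTBI if any single exposure meets these criteria". Exposures and mTBIs are therefore not the same count. However, the mTBI wording occurs only in the sentence sorting variables by type. Both statements of the model name blast exposures, which agrees with the randomisation paragraph.

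**Size of the smallest cells if eight are used.** The documents give neither the overall proportion of women nor the age or exposure split, so this is a range under assumptions: 3–15% women, 15–35% aged 40 or over, half with five or more exposures. With 120 participants, each of the two older-women cells would expect between 120 × 0.03 × 0.15 × 0.5 ≈ 0.3 and 120 × 0.15 × 0.35 × 0.5 ≈ 3 participants.

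**The case against.** The strongest reply is that this is a slip of one word. The plan says blocks are used within each stratum, which is ordinary stratified blocking. Read strata as factors, and the statistician makes one list per cell and every participant has exactly one list. No part of the plan describes one list per factor, a way of combining such lists, or anyone choosing between them. That is probably the intent, and it limits the consequences. It does not rescue the sentence, because the correct number still cannot be recovered: it is eight or four depending on whether age is a stratifier, and the sections disagree. The sample size text might be read as naming only those stratifiers thought to influence t-tau, but the analysis plan's list is closed and leaves age out.

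Four stronger readings are tempting, and the documents do not support them.

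- *Allocation is impossible or a promised balance is lost.* That follows only if three lists are actually used. The women and minorities sections promise women an equal chance of active drug, which any 1:1 list gives; they do not promise equal numbers.
- *The trial is biased or underpowered.* Chance imbalance does not bias a randomised comparison, the ANCOVA adjusts for gender and blast exposures in any case, and the stated power reproduces without any gain from stratification.
- *The imbalance can be quantified.* Any figure would need block sizes, proportions in each group and a rule for using three lists, none of which the plan gives.
- *The model adjusts for the wrong exposure count.* The model text twice names blast exposures; only the sentence sorting variables by type says otherwise.

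**Conclusion.** The number of strata is wrong as written: three is stated, against eight from the factors in the randomisation section or four from those in the sample size and analysis sections. This is a definite error in the allocation instruction, joined to an unresolved conflict over whether age is a stratifier. If carried out literally as one list per factor, there would be no rule for which list governs and balance within cells would not be assured. The likely cause is a slip of wording, and the damage is confined to that literal reading. The mTBI wording is a matter of terminology only.

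The strata count rests on the documents alone. The power check assumes a two-sided test. The remark on sparse cells rests on assumed proportions.

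**What to change.** Before the lists are generated, decide whether age is a stratification factor, state the factors once, and use them consistently.

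- **If age is kept:** in the randomisation paragraph write *each of the eight strata formed by crossing age, gender and number of blast trauma exposures*, and add age to the stratification variables in the sample size text and in both model statements of the primary analysis plan.
- **If age is dropped:** write *four* strata and remove age from the randomisation paragraph. The sample size and analysis text then already agree.
- **In either case:** in the sentence sorting variables by type, replace the reference to mTBIs with *number of blast trauma exposures (as recorded at randomisation)*, to match the model.

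The cost is a few words and the preparation of eight or four short lists. With eight cells, those for older women will hold very few participants and leave incomplete blocks. That is a small drawback, and the plan should record the choice between eight and four as deliberate.
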